7.3 Population characteristics

The following data will be recorded for each patient in a CRF:

- Age (years)
- Gender (male, female)
- Body weight (kg)
- Body height (cm)
- Medical and surgical history relevant to DOAC treatment
- Medication history – DOAC (type, dose, start of treatment, last intake before providing urine sample)
- Other medication history relevant to DOAC therapy
- Data will be taken from the patient's medical records.

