7	Factor Xa Inhibitors together Thrombin inhibitor Factor Xa inhibitors separately Apixaban Edoxaban Rivaroxaban	DOAC Dipstick DOASENSE Reader qualitative and quantitative LC-MS/MS	Interaction with demographic data
8	DOASENSE Control urines	DOAC Dipstick, DOASENSE Reader qualitative and quantitative	Descriptive Statistics Analysis of influence on parameters of DOAC Dipstick

Confidentiality Statement

This document is confidential and proprietary to Sponsor and HLZ Medizinische Statistik and for restricted circulation and access only. No part of it may be transmitted, reproduced, published or used by any person/s without prior written authorization.

9	Drop out	Demographic data, withdrawal of consent lack of dose, duration of therapy <7 days, Lack of results of DOAC Dipstick and of DOASENSE Reader No urine samples available at Limbach	Descriptive Statistics
10	Time dependence of results on test parameters	All test parameters of DOAC Dipsick	Descriptive statistics
11	Unexpected results	Examples: Non-compliance (LC_MSMS and DOAC Dipstick both negative) Factor Xa and thrombin inhibitor positive both with DOAC Dipstick and or LC-MSMS	Descriptive statistics
12	Questionnaire	Items	Descriptive Statistics parameters
13	Questionnaire Items	DOAC Dipstick	Interaction analysis

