- b. The results of dabigatran are analysed from group B as well as from group A to determine the statistical values.

Statistical methods: determination of a cut-off value with Logistic regression analysis, McNemar test, kappa index, accuracy, sensitivity, specificity, positive and negative predictive values.

V. Comparison of the **qualitative** results of the **DOASENSE Reader** with the **quantitative** results of **LC-MS/MS**. The results of Rivaroxaban, Apixaban and Edoxaban have to be analyzed separately because of different concentration ranges

Confidentiality Statement

This document is confidential and proprietary to Sponsor and HLZ Medizinische Statistik and for restricted circulation and access only. No part of it may be transmitted, reproduced, published or used by any person/s without prior written authorization.

during therapy by LC-MS/MS.

Statistical methods: determination of a cut-off value with Logistic regression analysis, McNemar test, kappa index, accuracy, sensitivity, specificity, positive and negative predictive values.

VI. Comparison of the **quantitative** results of the **DOASENSE Reader** with the **quantitative** results of **LC-MS/MS** is performed. The results of Rivaroxaban, Apixaban and Edoxaban have to be analyzed separately because of different concentration ranges during therapy by LC-MS/MS.

Statistical method: t-test.

VII. Analysis of an **interaction of demographic data** on the results of **DOAC Dipstick**, **DOASENSE Reader** and **LC-MS/MS** (demographic data, creatinine)

Statistical method: multivariable regression analysis using SELECTION=FORWARD method

VIII. Analysis **dose, last intake and duration of treatment** with each DOAC on **qualitative** results of **DOAC Dipstick** and **DOASENSE Reader** and **quantitative** results of **LC-MS/MS**

Statistical method: multivariable regression analysis using SELECTION=FORWARD method

IX. Analysis of an **interaction of demographic data** on the results of **DOAC Dipstick**, **DOASENSE Reader** and **LC-MS/MS** (demographic data, creatinine)

Statistical method: multivariable regression analysis using SELECTION=FORWARD method

X. Analysis **dose, last intake and duration of treatment** with each DOAC on **qualitative** results of **DOAC Dipstick** and **DOASENSE Reader** and **quantitative** results of **LC-MS/MS**

Statistical method: multivariable regression analysis using SELECTION=FORWARD method

Confidentiality Statement

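### The demographic regressions (items VII and IX) have no DOAC-type term but are also planned for the three factor Xa drugs pooled, so drug differences can show up as age, weight or sex effects

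*SAP*

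**What the plan says.** Section 10.2.2, items VII and IX (identical wording): "Analysis of an interaction of demographic data on the results of DOAC Dipstick, DOASENSE Reader and LC-MS/MS (demographic data, creatinine". The method is "multivariable regression analysis using SELECTION=FORWARD method". No term is forced in.

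Items VIII and X (also identical to each other) handle "dose, last intake and duration of treatment with each DOAC" in separate regressions.

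The label table in section 10.1.5, row 7, labelled "Interaction with demographic data", names these drug sets: "Factor Xa Inhibitors together Thrombin inhibitor Factor Xa inhibitors separately Apixaban Edoxaban Rivaroxaban". Its parameter column lists the Dipstick, the qualitative and quantitative Reader results, and LC-MS/MS.

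Items V and VI of section 10.2.2 say: "The results of Rivaroxaban, Apixaban and Edoxaban have to be analyzed separately because of different concentration ranges during therapy by LC-MS/MS". Item IV.a says the same of the strip comparison.

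Section 7.3 records, for each patient's DOAC, "type, dose, start of treatment, last intake before providing urine sample".

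**The concern.** The study is not randomised. Patients arrive on whichever DOAC they were prescribed, and users of the three factor Xa drugs may differ in age, weight or sex. The SAP itself says that urine concentrations differ between the drugs. When the drugs are pooled without a drug term, both conditions for confounding are present: drug is related to the outcome and may be related to the demographic predictor.

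Items VII and IX are meant to show whether patient characteristics change the strip, Reader or LC-MS/MS result. In the pooled run, a significant age coefficient could mean only that the older patients tended to be on the drug with the higher urine level. A reader could wrongly conclude that the device or drug excretion depends on age.

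The adjustment described in section 10.1.5 (propensity score) compares the factor Xa and thrombin inhibitor groups. It does nothing about differences among the three drugs within the factor Xa group.

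**Working it through.** **1. What the text fixes**

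| Place in SAP | Predictors or split | Drug sets |
|---|---|---|
| 10.2.2 items VII, IX | demographic data, creatinine | not stated |
| 10.2.2 items VIII, X | dose, last intake, duration | each DOAC |
| 10.1.5 label table, row 7 | demographic data | factor Xa pooled; thrombin inhibitor; each factor Xa drug |
| 10.2.2 items IV.a, V, VI | drugs kept apart for LC-MS/MS comparisons | each factor Xa drug |

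No described model holds demographics and DOAC type together. In the per-drug runs drug is constant, so the missing term matters only in the pooled run.

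**2. Size of the effect**

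The SAP states no figure to reproduce and gives no ages or concentrations by drug. From the SAP come the group size (440 less 12%: 440 × 0.88 = 387) and the two-sided 0.01 level. Everything else is assumed:

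- three drugs in equal thirds;
- log concentration with SD 1.0 within drug;
- age with SD 10 years within drug;
- no true age effect within any drug;
- highest-to-lowest mean concentration ratio *S* of 2, 3 or 5, and oldest-to-youngest mean age gap *G* of 2, 4 or 6 years, with the third drug midway.

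With *h* = ln(*S*)/2 and *g* = *G*/2:

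- covariance of age and log concentration between drugs: *C* = (2/3)·*g*·*h* if the two orders are fully aligned (the negative of this if fully reversed), and half that size if mixed;
- variance of age: *V* = 100 + (2/3)·*g*²;
- spurious slope per year: *C*/*V*;
- residual variance: *R* = 1 + (2/3)·*h*² − *C*²/*V*;
- standard error: √(*R*/(387·*V*));
- rejection rate: P(|Z + slope/SE| > 2.576).

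Worked case, 3-fold and 4 years, aligned: *h* = 0.549, *g* = 2, *C* = 0.732, *V* = 102.67. Slope = 0.00713 per year, or exp(0.0713) − 1 = 7.4% per decade. *R* = 1.196, SE = 0.00549, ratio = 1.30, rejection about 10%. Mixed order: the ratio falls to 0.65 and rejection to 2.8%.

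Rejection rate for age without a drug term:

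| Span | Order | 2 years | 4 years | 6 years |
|---|---|---|---|---|
| 2-fold | aligned or reversed | 1.7% | 4.4% | 9.7% |
| 2-fold | mixed | 1.2% | 1.7% | 2.7% |
| 3-fold | aligned or reversed | 2.8% | 10.1% | 25.7% |
| 3-fold | mixed | 1.4% | 2.8% | 5.3% |
| 5-fold | aligned or reversed | 4.5% | 20.4% | 50.7% |
| 5-fold | mixed | 1.8% | 4.4% | 9.9% |

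Of the six possible orderings of three drugs, one is aligned, one is reversed and four are mixed. Simulation agrees: 3-fold with 4 years gives about 10% (aligned or reversed) and 3% (mixed), and 5-fold with 6 years gives about 50% and 10%. With drug indicators in the model the simulated rate is about 1%, the nominal level.

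**3. What these rates do not show**

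Even in the worst cell, age explains little of the variance: *C*²/*V* = 1.609²/106 = 0.0244 out of 0.0244 + 1.407, or 1.7%. The calculation covers log concentration only. It leaves out creatinine, which the SAP includes, and forward selection, and nothing comparable was calculated for the strip result or Reader %REM.

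**The case against.** **The model is described in one line, and the term demographic data is not clearly defined.** Section 8.1 points to a paragraph that does not match the SAP's numbering. If section 7.3 is meant, its list includes DOAC type, dose and last intake, and row 1 of the label table puts demographics and dosing in one cell. So the text is loose. But section 6.3 lists demographic data and medication history as separate assessments, and items VIII and X would be redundant on the wide reading. Even on that reading, forward selection does not guarantee that drug enters the model.

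**Row 7 may not cross every drug set with every outcome.** It can be read as pooled for the shared factor Xa pad and separate for concentration. Table 19 in section 18 regresses biographic data on the strip's pads, and no listed table names LC-MS/MS on demographics. This is a fair reading. However, row 7 lists LC-MS/MS and quantitative Reader values beside the pooled set without restriction, and items VII and IX name LC-MS/MS as an outcome.

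**Dose and timing.** A reader might infer that leaving out dose and time since intake is an error of the same kind. The documents do not support that. Dose may be chosen partly from age or weight, so a model without it estimates the total association in patients as treated, which is a legitimate question for a point-of-care test. Simulations with assumed age-related dosing gave significant age coefficients in 6% to 58% of runs, but these are associations operating through dose and cannot simply be counted as false. What stands is that the SAP should say which association it wants.

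**Size.** A reader might also take the 50% figure as typical. It is the extreme cell and depends on full alignment or reversal.

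**Conclusion.** The point holds for the pooled factor Xa run and is minor. The SAP pools in row 7 what items IV.a, V and VI say must be separated, and names no drug term to make the pooling safe. That inconsistency needs no assumed figure. The direction and size of any bias cannot be derived from the SAP: the range of about 1% to 50% for a false age finding rests wholly on the assumed inputs, and falls to about 1% to 10% when the drug orders are mixed. The per-drug runs do not have the drug-type problem. The items are secondary, carry no decision rule, and leave the primary accuracy result untouched.

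**What to change.** In section 10.2.2, items VII and IX, and in label-table row 7:

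1. For the quantitative outcomes (LC-MS/MS on the log scale and Reader %REM), force DOAC type into any model that pools the factor Xa drugs before forward selection starts. Alternatively, drop the pooled model and report by drug.
2. Report the binary strip result by drug.
3. As a sensitivity analysis, repeat the quantitative models with daily dose and hours since last intake added. Label it as the association at a given dose and timing, and label the main model as the total association in patients as treated.
4. List the variables that count as demographic data, and correct the cross-reference in section 8.1.

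The cost is SAP wording, two degrees of freedom out of about 387 patients, and one extra model run. DOAC type, dose and last intake are already recorded under section 7.3.

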6.2. Determination of Sample Size

Two groups of medications (Thrombin inhibitor, Factor Xa inhibitors) will be tested with the IVD and test results compared to LC-MS/MS results in urine.

The objective of the investigation is to show that the proportion of false negative and false positive tests with the IVD is below 5%.

Confidentiality Statement

This document is confidential and proprietary to Sponsor and HLZ Medizinische Statistik and for restricted circulation and access only. No part of it may be transmitted, reproduced, published or used by any person/s without prior written authorization.

To improve the strength of the study result, the following adjustments were made in the version 3.0 of the SAP compared to the version 2.0: $\alpha=0.01$ and a 2-sided test with a null proportion of 0.01.

The re-calculation of the required sample size remained unchanged compared to version 2.0 of the document to show that the assumed rate of 2.5% false-negative/false-positive tests is statistically significantly lower than 5% would require 440 patients per each test group including an assumed drop-out rate of 12%, with $\alpha=0.01$ and $\beta=0.20$ (80% power).

This sample size has been assessed with the SAS procedure PROC POWER (SAS Institute Inc., Cary, NC, USA, release 9.3) using the ONESAMPLEFREQ statement under the assumption that the test will be conducted as a 2-sided test with a null proportion of 0.01.

Remark to the calculation of the anticipated dropout rate: **As the present post marketing study is a non-invasive investigation, the dropout rate may be lower than expected.** Only patients fulfilling all of the inclusion criteria and none of the exclusion criteria will be included. Patient's written informed consent is part of the inclusion criteria.

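### Forward selection, with no entry level and no forced terms, can leave dose, last intake or treatment duration without an adjusted estimate, although the SAP names all three for analysis

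*SAP*

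**What the plan says.** All places are in the SAP.

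- **Section 10.2.2, items VIII and X** (the same text twice): "Analysis dose, last intake and duration of treatment with each DOAC on qualitative results of DOAC Dipstick" and on the Reader, and also on the "quantitative results of LC-MS/MS". The method line is "multivariable regression analysis using SELECTION=FORWARD method".
- **Items VII and IX** (also duplicates) ask how patient characteristics bear on the strip, Reader and LC-MS/MS results. The candidates are given only as "demographic data, creatinine", and the method line is the same.
- No entry level, fixed candidate list or forced-in term is stated for any of these items.
- **Section 10.1.5** sets a general two-sided test level of 0.01 unless otherwise stated. It does not say that this is the entry criterion for selection.
- **Section 18** lists Table 20, on dependence of the results on time of last intake, and Table 21, on dose dependence for the individual DOACs.
- **Section 6.2 (sample size)** works from an "assumed rate of 2.5% false-negative/false-positive tests" and "440 patients per each test group including an assumed drop-out rate of 12" per cent.

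**The concern.** The analysis of dose, last intake and duration asks how large each effect is. Forward selection answers a different question, namely which factors pass a threshold in this dataset. A factor that does not pass drops out of the final model and has no adjusted estimate or interval. The reader then cannot tell a well-estimated null effect from one the data were too thin to show.

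A factor that does pass is reported because its estimate happened to be large, so its naive p-value and interval look better than they should.

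At stake is the adjusted answer on whether time since last intake, dose or duration changes the strip or Reader result.

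**Working it through.** **Inputs.** From section 6.2: 440 per group, 12% dropout, 2.5% assumed error rate. From section 10.1.5: general test level 0.01. From items VIII and X: three named factors per DOAC. Entry levels of 0.05 and 0.15 are assumptions that show a range, since the SAP states none.

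**The plan's own figure.** The SAP states no count of negative results. The 440 itself does not reproduce from its stated inputs: two-sided 0.01 and 80% power, with null variance, give 768 (873 with dropout) against a null of 5%, or 669 (761) against a null of 1%. That is a separate issue. The counts below are conditional on 440 being enrolled.

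**Step 1: proxy for sparse negatives.**
- Evaluable per group: 440 × 0.88 = 387.2.
- Expected errors: 387.2 × 0.025 = 9.7 (binomial 95% range 4 to 16).
- Per named factor: 9.7 / 3 = 3.2.
- If the Xa group split equally over three drugs (an assumption): 9.7 / 3 = 3.2 per drug.

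The modelled outcome is the test result, not an error. The 9.7 stands in for negatives on the patient's own pad if nearly all patients are truly positive. Non-adherent patients, listed among the unexpected results in section 10.1.5, would add negatives.

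**Step 2: chance that a real factor enters.** With event rate p among n patients, the standard error of a log odds ratio per SD is about 1/√(n p (1−p)) = 1/√(387.2 × 0.025 × 0.975) = 0.326. The factor enters with probability of about 1 − Φ(z − ln OR / SE), where z is 2.576 at entry 0.01 and 1.960 at 0.05.

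| True OR per SD | Entry 0.01 | Entry 0.05 |
|---|---|---|
| 1.5 (ln OR / SE = 1.25) | 9% | 24% |
| 2.0 (ln OR / SE = 2.13) | 33% | 57% |

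A simulation of the first selection step (n = 387, 2.5% events, 4,000 runs) gave about 9% and 23% for odds ratio 1.5, and 32% and 55% for 2.0.

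If 5% of patients were negative instead (387.2 × 0.05 = 19.4), the SE is 1/√(387.2 × 0.05 × 0.95) = 0.233. The same formula then gives 20% and 41% for odds ratio 1.5, and 65% and 84% for 2.0. A moderate effect would still be omitted more often than not.

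**Step 3: distortion of what does enter.** With 9.7 negatives, entry at 0.05 needs an estimated odds ratio of about exp(1.960 × 0.326) = 1.9 or more. Entry at 0.01 needs about exp(2.576 × 0.326) = 2.3 or more (or the reciprocals). A factor whose true odds ratio is 1.5 can therefore appear only with an overstated effect, or, rarely, one in the wrong direction.

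**Step 4: noise entry.** For k independent noise candidates at entry level a, the chance that at least one enters is 1 − (1 − a)^k. For k = 3:

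| a | Chance |
|---|---|
| 0.01 | 1 − 0.99³ = 3% |
| 0.05 | 1 − 0.95³ = 14% |
| 0.15 | 1 − 0.85³ = 39% |

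Sparse events do not drive this. The simulation at 2.5% events gave 2.7% for three candidates at 0.01, against 3.0% in theory. The rate depends on an entry level that the SAP leaves open.

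**The case against.** **The modelled outcomes are not errors.** Items VII to X model strip, Reader and LC-MS/MS results. An event count does not limit the quantitative LC-MS/MS outcome, which has about 387 observations per group. If items VII and IX pool the two groups, each pad should be mostly positive in one group and mostly negative in the other, so negatives would not be scarce. This stands, and it confines the sparse-data argument to the binary outcomes within a drug or group. Omission and post-selection distortion remain for every outcome.

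**A reader might infer that noise factors will often be selected.** The documents do not support that. At 0.01, the only test level the SAP gives, the chance is about 3% for three candidates. What can be said is that the rate is not controlled.

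**A reader might infer that the report would say nothing about last intake.** That goes too far. Tables 20 and 21 are planned, and section 10.1.5 plans descriptive statistics of dose, duration and last intake per DOAC. Only the adjusted estimate is at risk.

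**A reader might infer that the items worded as interactions go untested.** In context the word reads as influence on the result, and the SAP nowhere restricts the model to main effects. No point is made of it.

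**These are secondary analyses with no success criterion, and section 10.1.5 allows an unsuitable method to be replaced.** This limits the importance. However, the replacement would be chosen during the analysis, which is the situation a fixed model avoids.

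**Conclusion.** The point holds for items VIII and X. The SAP names three factors per DOAC but lets an unspecified threshold decide which of them are estimated, and this does not fit the tables it promises.

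Its size depends on the number of own-pad negatives. At about 10 per group, an effect of odds ratio 1.5 per SD would be left out in roughly three of four to nine of ten analyses, at entry levels 0.05 and 0.01. These figures rest on the 2.5% error rate as a proxy, on 440 being enrolled and on assumed entry levels. Further negatives from non-adherence make omission less likely, and splitting the Xa group by drug makes it more likely.

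The primary analysis is untouched. This is a cheap improvement.

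**What to change.** - **Items VIII and X:** for each DOAC, fit dose, time since last intake and duration together in one fixed model. Report all three estimates with intervals, whatever their p-values. Use Firth-penalised logistic regression where the binary outcome is sparse.
- **Items VII and IX:** fit the demographic variables already collected under section 7.3 (age, gender, weight, height) plus creatinine as a fixed set.
- **Forward selection:** keep it, if wanted, only as a labelled exploratory run with a stated entry level.

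The cost is a few lines in the SAP and one model option, with no extra data or patients. The price is less open-ended screening and wide intervals where negatives are few, but those intervals show honestly how little the data can say.

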8. DEFINITIONS AND DERIVED VARIABLES

All measurements are carried out according to standard medical methods of the investigational site. The personnel involved are adequately trained in required measurements.

Patients will collect a sample of urine into the container provided by DOASENSE GmbH and hand it over to the site personnel.

The site personnel will first perform

- 1) Visual testing using DOAC Dipstick according to the instructions for use (annex 2)

Confidentiality Statement

This document is confidential and proprietary to Sponsor and HLZ Medizinische Statistik and for restricted circulation and access only. No part of it may be transmitted, reproduced, published or used by any person/s without prior written authorization.

Sponsor Name: DOASENSE GmbH
Statistical Analysis Plan (SAP)
Version No.: 3 Date: 2019-05-15

Sponsor Study No.: DOA-CS-002
ClinicalTrials.gov ID: NCT03182829
HLZ Medizinische Statistik Study No.: 1-2019

- 2) immediately thereafter analyze the patient's DOAC Dipstick with the DOASENSE Reader (annex 3). The printout of the DOASENSE Reader is attached to the respective field in the CRF with the numbers to be written with a pencil beside the printout because the thermopaper of the printout may lose colour over time.
- 3) put two aliquots of 5 mL urine into the tubes provided for measurements of DOACs and creatinine.
- 4) to discard the remaining urine.
- 5) Analysis of DOASENSE Control Urines that comprise a negative and positive control for DOACs and creatinine before and after inclusion of every 12th patient
- 6) Compilation of a questionnaire on the handling of DOAC Dipstick and its analysis by the study personnel that perform the test (visual and with DOASENSE Reader) after having performed the analyses of the 5th and 15th patient

All sites will receive the same model/type of reflectance photometric dipstick color reader (DOASENSE Reader).

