8.4 Analysis by LC-MS/MS

Urine samples will be analyzed at Laboratory Limbach by LC-MS/MS. The method is described elsewhere (23). The results are given as ng/ml. Normal range of values is 0.1 to 4.0 ng/ml (23). Normal values are interpreted as “negative”. Higher values represent “positive” results. Optionally, the upper limit of normal range may be changed to 8 ng/ml if values between 4 ng/ml and 8 ng/ml occur in more than 0.5% of patients.

Methodological reasons may lead to a repeated measurement of the urine sample diluted 1:15. Analyses will be repeated with this dilution if concentration of DOAC in urine is > 50.000 ng/ml or is expected to be above this value. The repetition is required to ensure that the concentration is in the linear range of detection range of LC-MS/MS. However, the dilution affects the normal range, which is 15-fold higher compared to samples that are

Confidentiality Statement

This document is confidential and proprietary to Sponsor and HLZ Medizinische Statistik and for restricted circulation and access only. No part of it may be transmitted, reproduced, published or used by any person/s without prior written authorization.

analysed without this dilution. For the statistical evaluation these mean of the normal range without dilution will be used.

Remark: The personal at Limbach laboratory is blinded regarding the information which DOAC the patient is taken. The personal does not have access to any information in the CRF which DAOC the patient was taking.

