8.8 Clinical Efficacy and Safety Endpoints

This is a non-interventional study to determine the accuracy of the IVD DOAC Dipstick in comparison to the concentration of the analytes in spontaneously obtained urine sample of patients on chromic treatment with DOACs. Clinical endpoints are not part of the determination of the accuracy of DOAC Dipstick in the study.

The patients will not have additional risks due to participation in the investigation, and will not benefit directly by participating. Only patients who already take oral direct Factor Xa or Thrombin inhibitors will be included into the trial. They will provide a spontaneous urine sample for testing and will not come into contact with the test itself.

Therefore, clinical efficacy and safety endpoints are not defined for this study.

Confidentiality Statement

This document is confidential and proprietary to Sponsor and HLZ Medizinische Statistik and for restricted circulation and access only. No part of it may be transmitted, reproduced, published or used by any person/s without prior written authorization.

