18. LIST OF POST-TEXT-TABLES

Per protocol analysis

Tables

1. Demographic data of patients of group A and Group B, p values
2. Descriptive data of tested parameters per group
3. Results of regression analysis for Rivaroxaban with LC-MC/MC
4. Results of Regression analysis for Dabigatran with LC-MC/MC
5. Results of Regression analysis for Creatinine Jaffe Method
6. Results of Regression analysis of Urine Colour (REM% values)
7. Group A: correct and false negative and positive data of DOAC Dipstick versus LC-MS/MS, p-value
8. Group B: correct and false negative and positive data of DOAC Dipstick versus LC-MS/MS, p-values
9. Apixaban: correct and false negative and positive data of DOAC Dipstick versus LC-MS/MS, p-value
10. Edoxaban: correct and false negative and positive data of DOAC Dipstick versus LC-MS/MS, p-value
11. Rivaroxaban: correct and false negative and positive data of DOAC Dipstick versus LC-MS/MS, p-values
12. Group A: Creatinine: correct and false of low and normal data of DOAC Dipstick versus Jaffe-Method, p-value
13. Group B: Creatinine: correct and false of low and normal data of DOAC Dipstick versus Jaffe-Method, p-value
14. All analyses of no 3 to 13 with qualitative results DOAC Dipstick versus quantitative Results of DOAC Dipstick
15. Comparison of negative and positive or low and normal results of all pads of DOAC

Confidentiality Statement

This document is confidential and proprietary to Sponsor and HLZ Medizinische Statistik and for restricted circulation and access only. No part of it may be transmitted, reproduced, published or used by any person/s without prior written authorization.

Dipstick versus DOASENSE Reader

16. Comparison of quantitative values of all pads by DOASENSE Reader versus LC-MS/MS and Jaffe Method
17. Interaction of Apixaban, Edoxaban and Rivaroxaban results of DOAC Dipstick with results of Creatinine of DOAC Dipstick
18. Interaction of Apixaban, Edoxaban and Rivaroxaban and creatinine results of DOAC Dipstick with results of urine colour of DOAC Dipstick
19. Regression analysis of biographic data with pads of DOAC Dipstick to test interactions
20. Results of dependence of time of last intake of or drug on DOAC Dipstick quantitative, DOASENSE Reader qualitative and quantitative, and LC-MS/MS
21. Results of dose dependence of individual DOACs on parameters of No 20
22. Descriptive results of DOASENSE Control Urines and analysis of differences between centres

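### The dose and last-intake analyses of spot-urine DOAC concentration omit the urine creatinine measured in the same sample; an adjusted model should stand beside the unadjusted one

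*SAP*

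**What the plan says.** All references are to the SAP.

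- **Dose analysis.** Section 10.2.2, items VIII and X, names "dose, last intake and duration of treatment" as predictors of the qualitative dipstick and Reader results and of the quantitative LC-MS/MS result, for each DOAC. Creatinine is not listed.
- **Creatinine analysis.** Items VII and IX of the same section cover "demographic data, creatinine" and do not list dose or last intake.
- **Method.** Each of the four items has its own "multivariable regression analysis using SELECTION=FORWARD method". Item IX repeats VII and item X repeats VIII, here and in section 9.2.1.
- **Outcome.** Section 8.4 sets the unit: "The results are given as ng/ml". No creatinine-corrected or log scale is defined.
- **Sample.** Section 8.8 says of the patients: "They will provide a spontaneous urine sample for testing".
- **Creatinine is available.** Section 8 has site staff "put two aliquots of 5 mL urine into the tubes provided for measurements of DOACs and creatinine", and section 8.5 specifies the Jaffe method for creatinine at the central laboratory.
- **Tables.** In section 18, Table 20 covers time of last intake and Table 21 is "Results of dose dependence of individual DOACs on parameters of No 20". Neither mentions creatinine. Table 17 brings creatinine in only as a dipstick result set against dipstick results of the three factor Xa drugs.

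**The concern.** A drug concentration in spot urine depends on how much drug is excreted and on how much water it is excreted in. Two patients with the same dose, intake time and excretion can therefore give different ng/ml values. Creatinine in the same urine carries part of that variation, and the SAP will have it.

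Because creatinine and dose sit in separate models, no listed analysis estimates the dose or last-intake effect with creatinine held fixed. The SAP itself treats creatinine as relevant to the drug result: section 8.2 says that the DOAC pads may be falsely negative when it is low, and reads low creatinine as renal insufficiency.

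At stake are the precision of the dose and last-intake estimates for LC-MS/MS in Tables 20 and 21 and, under a further condition, their freedom from confounding.

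**Working it through.** The SAP states no power or precision for items VIII and X, so there is no figure of its own to reproduce. What follows is an illustration on the natural-log scale.

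**Inputs from the SAP**
- 440 patients per group with 12% dropout (Determination of Sample Size): 440 × 0.88 ≈ 387 evaluable.
- Two-sided alpha 0.01 (section 10.1.5), so z = 2.576.

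**Assumptions (not in the SAP)**
- SD of ln creatinine, s: 0.6, range 0.5 to 0.8.
- Other residual SD, r: 0.8.
- Slope b of ln drug concentration on ln creatinine: 1 (full proportionality) or 0.5.
- Two doses 2-fold apart, split 50:50, concentration proportional to dose.
- Patients on one drug: 387 (dabigatran, the only thrombin inhibitor), 130 (about 387/3, an equal split of the factor Xa group) or 65 (a smaller subset).

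**Step 1: gain in precision.** Share of residual variance removed = b²s² / (b²s² + r²). Narrowing of intervals = 1 − √(1 − share).

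| b | s | Share removed | Intervals narrower by |
|---|---|---|---|
| 1 | 0.5 | 0.25/0.89 = 28% | 15% |
| 1 | 0.6 | 0.36/1.00 = 36% | 20% |
| 1 | 0.8 | 0.64/1.28 = 50% | 29% |
| 0.5 | 0.6 | 0.09/0.73 = 12% | 6% |

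The range of 6% to 29% holds at r = 0.8. A smaller r gives a larger gain: with b = 1, s = 0.8 and r = 0.5, the unadjusted standard error is √(0.64 + 0.25)/0.5 = 1.89 times the adjusted one.

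**Step 2: power for a 2-fold dose effect** (ln 2 = 0.693), by normal approximation: power = Φ(0.693 / (SD × √(4/n)) − 2.576). SD is √(b²s² + r²) without creatinine and r with it. For b = 1 and r = 0.8:

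| n on one drug | Unadjusted, s = 0.6 | Unadjusted, s = 0.8 | Adjusted |
|---|---|---|---|
| 65 | 0.59 | 0.46 | 0.82 |
| 130 | 0.92 | 0.82 | 0.99 |
| 387 | 1.00 | 1.00 | 1.00 |

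With b = 0.5 and s = 0.6 at n = 65, SD = √0.73 = 0.854, and unadjusted power is Φ(0.693/0.212 − 2.576) = Φ(0.69) ≈ 0.76, against 0.82 adjusted.

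**Step 3: bias.** If dilution is unrelated to dose and intake time, the expected bias is nil. If mean ln dilution differs by d between the dose groups, a true 2.0-fold effect is estimated as 2.0 × e^(±d). For d = 0.1 this is 2.2 or 1.8; for d = 0.3 it is 2.7 or 1.5. The SAP gives no value for d.

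**The case against.** **The uncorrected concentration is a legitimate target.** The study tests a dipstick against the analyte concentration "in spontaneously obtained urine sample of patients", and the strip is dipped into that same urine. How dose and last intake relate to the concentration in the cup is a coherent question, and a creatinine-adjusted coefficient answers a somewhat different one. This stands, and it is why the unadjusted estimate must stay.

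**Creatinine is not a pure marker of dilution.** The SAP reads low values as renal insufficiency and never mentions hydration. This also stands, and it too calls for showing both estimates.

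**Dilution need not swamp the dose effect.** A reader might set 0.25 g/l (section 8.5) against 1.5 g/l (section 8.6), a 6-fold span, and infer that dilution varies more than dose. The first figure is a cut-off between low and normal, and the second is the content of a manufactured control urine. Neither describes patients, and the SAP gives no spread of dose in this trial.

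**The repeated items need not mean repeated analyses.** A reader might infer that each model is run twice. Tables 19 to 21 list the demographic, last-intake and dose analyses once each, so the repetition looks clerical.

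**The SAP allows additional evaluations.** It does, but a general permission does not pre-specify this model.

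**Conclusion.** The point holds as a cheap improvement to secondary analyses, not as the correction of an error. Items VIII and X leave out a covariate that is measured in the same urine and that the SAP itself links to the drug result. The listed tables do not repair the split.

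The cost of the omission is mainly noise. Under the stated assumptions, adjustment narrows intervals by about 6% to 29%, depending on the spread of creatinine and on how closely drug concentration scales with it. The loss matters mainly in small single-drug factor Xa subsets: at 65 patients, power for a 2-fold effect falls from 0.82 to 0.46 in the least favourable case computed and to about 0.76 at a slope of 0.5. At about 387 patients it is negligible.

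A reader might also infer that the planned dose estimates are biased. That needs creatinine to be associated with dose or intake time, which the SAP neither states nor excludes. The units issue concerns only the LC-MS/MS outcome; items VIII and X also model qualitative dipstick and Reader results. The primary endpoint is unaffected.

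**What to change.** 1. Delete items IX and X, which duplicate VII and VIII, in sections 9.2.1 and 10.2.2, and renumber.
2. Keep the unadjusted analysis in item VIII. Add, per DOAC, a linear model of log LC-MS/MS concentration on dose, time since last intake and duration, with log Jaffe creatinine, age, sex and weight forced in. Forward selection could otherwise drop creatinine in exactly the small subsets where it helps most.
3. Show both estimates with confidence intervals side by side in Tables 20 and 21. State that the adjusted one holds urine creatinine fixed and that creatinine also reflects muscle mass and renal function.
4. State how values too low to log-transform are handled.

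The cost is SAP wording and one added model per drug, offset by the two deleted items. No new data or samples are needed. The downside is a second coefficient with a somewhat different meaning, which the report has to explain.
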